### Appendix D. BI-RADS Classification

The BI-RADS assessment categories are:

- 0 Incomplete,
- 1 Negative,
- 2 Benign findings,
- 3 Probably benign,
- 4 Suspicious abnormality,
- 5 Highly suspicious of malignancy,
- 6 Known biopsy with proven malignancy

# 1.0 Introduction

This Statistical Analysis Plan (SAP) describes the statistical analyses for Study M16-283" A Phase 3b Study to Evaluate the Long-Term Safety of Elagolix in Combination with Estradiol/Norethindrone Acetate for the Management of Heavy Menstrual Bleeding Associated with Uterine Fibroids in Premenopausal Women."

Study M16-283 examines the long-term safety of elagolix 300 mg administered twice daily (BID) in combination with estradiol 1 mg/0.5 mg norethindrone acetate (E2/NETA 1 mg/0.5 mg) in premenopausal women with heavy menstrual bleeding associated with uterine fibroids.

The analyses of pharmacokinetic endpoints, pharmacodynamic biomarker endpoints and exploratory research endpoints will not be covered in this SAP.

The SAP will not be updated in case of administrative changes or amendments to the protocol unless the changes impact the analysis.

Unless noted otherwise, all analyses will be performed using SAS Version 9.4 (SAS Institute Inc., Cary, NC 27513) or later under the UNIX operating system.

# 2.0 Study Design, Objectives and Procedures

## 2.1 Objectives

The objectives of this study are to:

- Assess the safety of elagolix 300 mg administered twice daily (BID) in combination with E2/NETA (estradiol 1.0 mg/norethindrone acetate 0.5 mg QD) compared to placebo at 12 months in premenopausal women with heavy menstrual bleeding associated with uterine fibroids,
- Characterize the impact of elagolix 300 mg BID with E2/NETA on bone mineral density (BMD) in women with HMB associated with uterine fibroids after up to 48 months of treatment.

## 2.2 Study Design Overview

This Phase 3b, randomized, 12-month double-blind placebo-controlled, 36 month openlabel, multi-center study is designed to evaluate the safety of elagolix with add-back therapy in women with HMB associated with uterine fibroids.

Approximately 500 subjects will be randomized in a 2:1 ratio to one of the following 2 treatment groups:

- Elagolix 300 mg BID plus E2/NETA (estradiol 1.0 mg/norethindrone acetate 0.5 mg QD) (n = 333) for 48 months
- 2. Placebo (n = 167) for 12 months

Subjects randomized to elagolix 300 mg BID plus E2/NETA in the 12-month Treatment Period will receive the same treatment during the open-label Treatment Period. Subject randomized to placebo in the 12-month Treatment Period will switch to elagolix 300 mg BID plus E2/NETA during the open-label Treatment Period after completing the 12-month Treatment Period.

The total duration for a subject's participation in this study is approximately 77 months, consisting of the following 4 study periods:

- 1. Washout Period up to 10 months prior to Screening (only applicable if subject is taking exclusionary medication at the time of consent; duration of washout depends on the type of exclusionary medication being taken).
- 2. Screening Period approximately 2.5 to 5 months prior to first dose of study drug.
- 3. Treatment Period up to 48-month treatment duration
- 4. Post-Treatment Follow-Up Period up to 12 months duration following the last dose of study drug. Subjects are expected to enter Post-Treatment Follow-Up after completing Treatment Period Month 48, or at any time a subject prematurely discontinues during the Treatment Period.

The Study Schematic is shown below in Figure 1.

#### Figure 1. Study Schematic

#### SCREENING AND TREATMENT PERIOD

PTFU = Post-Treatment Follow-Up

#### Figure 1.Study Schematic (Continued)

#### TREATMENT AND POST-TREATMENT FOLLOW-UP PERIOD

## 2.3 Treatment Assignment and Blinding

Approximately 500 subjects will be randomily assigned in a 2:1 ratio to one of the following 2 treatment groups:

- Elagolix 300 mg BID plus E2/NETA (estradiol 1.0 mg/norethindrone acetate 0.5 mg QD) (n = 333)
- 2. Placebo (n = 167)

Unless otherwise specified, data will be summarized by group as listed above.

## 2.4 Sample Size Determination

Approximately 500 subjects will be randomily assigned (2:1) to elagolix 300 mg BID plus E2/NETA (N = 333) and placebo (N = 167).

Based on clinical review, a sample size of 500 was selected to gather long term safety exposure data in approximately 50 subjects completing 48 months of study drug dosing, with approximately 30 subjects receiving 48 months of active drug elagolix 300 mg BID plus E2/NETA 1/0.5 mg QD.

## 2.5 End of 12-Month Placebo-Controlled Treatment Period Analysis

An end-of-placebo-controlled treatment period analysis will be performed after the last subject completes the 12-Month placebo-controlled Treatment Period. These analyses will include data collected during the full Treatment Period (placebo-controlled and openlabel Treatment Periods) and the Follow-Up Period up to the data cut-off for the interim lock. The database will be versioned for an interim lock and any discrepant data will be clarified before the versioning. Analyses will be performed by AbbVie.

Since this end-of-placebo-controlled treatment period analysis is the only and final analysis for the comparison between treatment and placebo group at 12 months of safety and efficacy endpoints, no additional adjustment of alpha-level is necessary.

## 2.6 Treatment Month 24, Month 36 and Month 48 Analyses

At the end of Treatment Month 24, Month 36 and Month 48, analysis of the safety and efficacy safety variables may be performed after the last subject completes the Treatment Month 24, Month 36 and Month 48 visit, respectively. For subjects who prematurely discontinued during the treatment period, their data collected during the Follow-up Period will be included in the analysis, as appropriate. The database will be versioned for an interim lock and any discrepant data will be clarified before the versioning. Analyses will be performed by AbbVie.

# 3.0 Endpoints

## 3.1 Primary Endpoint

As the objective of this study is to evaluate the long-term safety and tolerability of elagolix 300 mg BID with E2/NETA, no primary efficacy endpoint is defined.

## 3.2 Secondary Endpoint

As the objective of this study is to evaluate the long-term safety and tolerability of elagolix 300 mg BID with E2/NETA, no secondary efficacy endpoint is defined.

## 3.3 Other Efficacy Endpoints

Other efficacy endpoints include the following:

- PGIC for Menstrual Bleeding Symptom at Month 3, Month 6, Month 9 and Month 12;
- Change from baseline for the UFS-QoL at Month 6 and Month 12.

## 3.4 Safety Endpoints

The safety endpoints will be based on the following evaluations:

- Dual energy X-ray absorptiometry (DXA) scan
- Adverse events monitoring
- Clinical laboratory tests
- Vital signs
- Endometrial biopsy
- Pelvic ultrasound (transabdominal ultrasound [TAU]/transvaginal ultrasound [TVU])
- Columbia Suicide Severity Rating Scale (C-SSRS)
- Pregnancy

# 4.0 Analysis Populations

The Full Analysis Set (FAS) is composed of all randomized subjects who have received at least 1 dose of study drug in this study. The data from the FAS will be presented by the treatment group assigned at the time of randomization, even if a subject does not receive the correct treatment or does not follow the protocol until completion. The FAS will be used for all efficacy and baseline analyses unless otherwise specified in the SAP. Subjects who do not continue into the open-label Treatment Period will be excluded from the analyses in the open-label Treatment Period.

The following populations will be used for safety analyses:

- The Safety Analysis Set includes all randomized subjects who received at least 1 dose of study drug. Subjects will be analyzed according to the treatment they actually receive, defined as the randomized treatment if the patient took at least one dose of that randomized treatment during the 12-month placebo-controlled double-blind Treatment Period, or the first treatment received if the randomized treatment was never received during the 12-month placebo-controlled doubleblind Treatment Period. Subjects who do not continue into the open-label Treatment Period will be excluded from the analyses in the open-label Treatment Period.
- The All Elagolix plus E2/NETA Analysis Set is defined as subjects who received at least 1 dose of elagolix plus E2/NETA in the study (either in the placebo-controlled or open-label Treatment Periods). Subjects will be summarized based on the actual treatment received at the time of randomization (elagolix plus E2/NETA or placebo).

# 5.0 Subject Disposition

A summary of subject accountability will be provided where the number of subjects in each of the following categories will be summarized for all randomized subjects by treatment group and overall:

• Subjects randomized in the study.

- Subjects who took at least one dose of study drug.
- Subjects who completed the placebo-controlled Treatment Period.
- Subjects who prematurely discontinued during the placebo-controlled Treatment Period.
- Subjects who entered into the open-label Treatment Period.
- Subjects who prematurely discontinued during the open-label Treatment Period.
- Subjects who completed protocol-specified treatment.
- Subjects who prematurely discontinued study drug (all reasons and primary reason).
- Subjects who entered into the Follow-up Period.
- Subjects who completed the Follow-up Period.

The number and percentage of subjects who discontinued study drug will be summarized by treatment group and overall as follows based on the Full Analysis Set:

- By any reason for discontinuation
- By primary reason for discontinuation

In addition, the number and percentage of subjects who discontinued study will be summarized for the FAS by treatment group and overall as follows:

- By any reason for discontinuation
- By primary reason for discontinuation

# 6.0 Study Drug Duration

Duration (days) of treatment will be summarized for the Safety Analysis Set using the number of subjects treated, mean, standard deviation, median, minimum and maximum.

Study drug duration will be summarized as follows:

#### Placebo-controlled Treatment Period (Safety Analysis Set):

Duration of treatment during the placebo-controlled Treatment Period is defined as follow:

- For subjects who did not continue into the open-label Treatment Period:
  - Last dose date during the placebo-controlled Treatment Period First dose date during the placebo-controlled Treatment Period + 1
- For subjects who continued into the open-label Treatment Period: Minimum of
  - Last dose date during the placebo-controlled Treatment Period First dose date during the placebo-controlled Treatment Period + 1
  - First dose date during the open-label Treatment Period First dose date during the placebo-controlled Treatment Period.

In addition, the number and percentage of subjects in each treatment duration interval  $(1 - < 28 \text{ days}, 28 - < 56 \text{ days}, 56 - < 84 \text{ days}, 84 - < 112 \text{ days}, 112 - < 140 \text{ days}, 140 - < 168 \text{ days}, 168 - < 196 \text{ days}, 196 - < 224 \text{ days}, 224 - < 252 \text{ days}, 252 - < 280 \text{ days}, 280 - < 308 \text{ days}, 308 - < 336 \text{ days}, \ge 336 \text{ days})$  will be summarized.

#### **Open-label Treatment Period (Safety Analysis Set):**

Duration of treatment during the open-label Treatment Period is defined as last dose date during the open-label Treatment Period minus first dose date during the open-label Treatment Period plus 1 day.

In addition, the number and percentage of subjects in each treatment duration interval  $(1 - < 84 \text{ days}, 84 - < 168 \text{ days}, 168 - < 252 \text{ days}, 252 - < 336 \text{ days}, 336 - < 420 \text{ days}, 420 - < 504 \text{ days}, 504 - < 588 \text{ days}, 588 - < 672 \text{ days}, 672 - < 756 \text{ days}, 756 - < 840 \text{ days}, 840 - < 924 \text{ days}, 924 - < 1008 \text{ days}, \ge 1008 \text{ days})$  will be summarized.

#### All Elagolix plus E2/NETA Analysis Set:

For subjects who received at least 1 dose of elagolix plus E2/NETA (either in the placebocontrolled or open-label Treatment Period), the duration of treatment is defined as the last dose date of receiving elagolix plus E2/NETA minus the first dose date of receiving elagolix plus E2/NETA plus 1 day.

In addition, the number and percentage of subjects in each treatment duration interval  $(1 - < 84 \text{ days}, 84 - < 168 \text{ days}, 168 - < 252 \text{ days}, 252 - < 336 \text{ days}, 336 - < 420 \text{ days}, 420 - < 504 \text{ days}, 504 - < 588 \text{ days}, 588 - < 672 \text{ days}, 672 - < 756 \text{ days}, 756 - < 840 \text{ days}, 840 - < 924 \text{ days}, 924 - < 1008 \text{ days}, 1008 - < 1092 \text{ days}, 1092 - < 1176 \text{ days}, 1176 - < 1260 \text{ days}, 1260 - < 1344 \text{ days}, \ge 1344 \text{ days})$  will be summarized.

# 7.0 Demographics, Baseline Characteristics, Medical History, and Prior/Concomitant Medications

Demographics, baseline characteristics, medical history, prior medications, concomitant medications, and post-treatment medications will be summarized by treatment group and overall using the Full Analysis Set. Categorical variables will be summarized with the number and percentage of subjects; percentages will be calculated based on the number of non-missing observations. Continuous variables will be summarized with descriptive statistics (number of non-missing observations, mean and standard deviation, median, minimum and maximum).

#### 7.1 Demographics and Baseline Characteristics

Continuous demographic variables include age, weight, height, and body mass index (BMI). Categorical demographic variables include sex, ethnicity, race, age (18 – 19, 20 - 24, 25 - 29, 30 - 34, 35 - 39, 40 - 44, 45 - 49,  $\geq 50$  years), BMI ( $\leq 18.5$ , > 18.5 - <25,  $\geq 25 - <30$ ,  $\geq 30 - <35$ ,  $\geq 35 - <40$ ,  $\geq 40$  kg/m^2), tobacco use (current, former, never, unknown), and alcohol use (current, former, never, unknown).

## 7.2 Medical History

Medical history and gynecological medical/surgical history data will be coded using the Medical Dictionary for Regulatory Activities (MedDRA). The actual version of the MedDRA coding dictionary will be noted in the statistical tables and clinical study report. The number and percentage of subjects in each medical history category (by MedDRA system organ class and preferred term) will be summarized by treatment group and overall for the FAS. The system organ class (SOC) will be presented in alphabetical order, and the preferred terms will be presented in alphabetical order within each SOC. Subjects reporting more than one condition/diagnosis will be counted only once in each row (SOC or preferred term).

## 7.3 Prior, Concomitant, and Post-Treatment Medications

Prior, concomitant, and post-treatment medications will be summarized by generic name for the FAS.

Prior medications are those medications with a start date prior to the first study drug administration date. Prior medications will be summarized separately for each treatment group and overall using ATC Classification and preferred terms from the World Health Organization (WHO) Drug Dictionary.

Concomitant medications are those medications, other than study drugs, taken during the treatment period with an end date after the first dose of study drug or ongoing at the end of study, and a start date prior to the last dose of study drug. A medication will be considered a concomitant medication if any of the following three cases occur (1) the start date is missing and the end date is either after or on the first study drug dose date; (2) the start date is not missing and the end date is missing; (3) both the start date and the end date are missing.

Concomitant medications will be summarized using ATC Classification and preferred terms from the World Health Organization (WHO) Drug Dictionary with number and percentage for each treatment group and overall.

Post-treatment medications are those medications with an end date after the last dose of study drug or ongoing at the end of study. Post-treatment medications will be summarized by ATC Classification and WHO preferred term with number and percentage for each treatment group and overall.

A subject who reports two or more uses of the same medication will be counted only once within each WHO preferred term. A subject with medications with more than one generic name will be counted only once in the overall total. Prior medications, concomitant medications, and other medications during the Post-Treatment Follow-up Period will be summarized separately.

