## 5.2.3.2 Concomitant Therapy

All other medications or vaccines (including over-the-counter or prescription medicines, vitamins and/or herbal supplements) that the subject is receiving at the time of entering into the Washout Period (if required) or Screening Period and during the Treatment and Post-Treatment Follow-Up Periods must be recorded in source documents and on the Concomitant Medication eCRFs. The reason for use, date(s) of administration (including start and end dates) and dosage information (including dose and frequency) must be recorded.

Given the ongoing COVID-19 pandemic, selected non-live vaccines (e.g., mRNA, non-replicating viral vector, protein subunit, etc.) to prevent SARS-CoV-2 infection may be administered during the Treatment and Post-Treatment Follow-Up Periods, as long as components of the vaccine are not contraindicated.

The decision to receive a locally available vaccine should be based on local guidance and an individual discussion between the treating physician and the subject.

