## 5.2.3.5 Prohibited Therapy

All hormonal forms of birth control (except the emergency contraceptive pill, levonorgestrel 1.5 mg [such as Plan B®], or ulipristal acetate 30 mg [such as Ella® or EllaOne®]) are prohibited during the Washout, Screening, Treatment Periods and until the Post-Treatment Follow-Up Period Month 1. Subjects may start hormonal contraception after completion of Post-Treatment Follow-Up Period Month 1, and having a negative urine pregnancy test after 1 month off of study drug and returned to menses. If the Subject has not returned to menses by Month 1 in the Post-Treatment Follow-Up Period, the Investigator would use acceptable medical practice to reinitiate hormonal contraceptive (e.g., pregnancy test, FSH, induction of withdrawal bleed, etc.).

For subjects who are prescribed/administered the emergency contraceptive pill during the study, the information should be captured in the source documents and eCRF and the AbbVie TA MD must be informed.

Tranexamic acid should not be taken during the Screening and Treatment Periods, however tranexamic acid, if necessary, can be prescribed following completion of the Treatment Period and the subject has returned to first full menses. Should the subject be prescribed tranexamic acid during the Treatment Period, they will be discontinued and will enter the Post-Treatment Follow-Up Period.

Any supplements or herbal remedies used to treat premenstrual or gynecological problems, such as black cohosh, are excluded.

The following medications should not be taken during the Washout (if applicable), Screening, and the Treatment Periods.

[figure not shown]
[figure not shown]

Table 3. Prohibited Medications

GnRH agonist	Leuprolide acetate (Lupron®)	
Prohibited During the Washout, Screening and Treatment Periods and Through Follow-Up Month 1		
Hormonal and Non-hormonal Estrogen Supplements, ** such as:	GnRH agonists: nafarelin acetate (Synarel®), goserlin acetate (Zoladex®)	
	GnRH antagonists (other than study elagolix)	
	Danazol (Danocrine®, Cyclomen®)	
	Medroxyprogesterone acetate (Depo-Provera®, Provera®)	
	Oral contraceptives	
	Estrogen preparations*	
	Testosterone preparations	
	Other progestins* (oral, vaginal, transdermal, implantable, IUD, or LNG-IUS, except emergency contraception)	
	HCG or HCG products	
	Glucocorticoids, oral or injectable (chronic use only)	
	Other progestins (oral, vaginal, IUDs, implantable)	
	Levonorgestrel (except emergency contraception, i.e., levonorgestrel 1.5 mg)	

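### SAP 7.3 contradicts itself: case (2) of the concomitant-medication rule drops the start-date limit set one sentence earlier, so an open-ended drug begun in follow-up could be listed as concomitant

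*SAP*

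**What the plan says.** SAP 7.3 (Prior, Concomitant, and Post-Treatment Medications) defines concomitant medications in two consecutive sentences.

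- **General definition.** These are non-study drugs used on treatment whose end date falls later than the first dose. The sentence finishes with the alternative to an end date and with the start-date limit: "ongoing at the end of study, and a start date prior to the last dose of study drug".
- **Missing-date cases.** "A medication will be considered a concomitant medication if any of the following three cases occur": (1) start date missing and end date on or after the first dose; (2) "the start date is not missing and the end date is missing"; (3) both dates missing.

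The same section defines the post-treatment category with no condition on the start date: "Post-treatment medications are those medications with an end date after the last dose of study drug or ongoing at the end of study". It closes by asking for separate presentation: "Prior medications, concomitant medications, and other medications during the Post-Treatment Follow-up Period will be summarized separately".

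The protocol makes the situation possible. Section 5.2.3.2 says that medications taken "during the Treatment and Post-Treatment Follow-Up Periods must be recorded in source documents and on the Concomitant Medication eCRFs", so follow-up drugs sit in the same dataset as on-treatment drugs. Section 5.2.3.5 states "Subjects may start hormonal contraception after completion of Post-Treatment Follow-Up Period Month 1", subject to a pregnancy test and return of menses. It also allows tranexamic acid once treatment is complete and menses have returned. Appendix C schedules a medication review at follow-up Months 1, 6 and 12.

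**The concern.** Case (2) asks only whether a start date is present and an end date absent. A drug begun months after the last dose and still in use can satisfy it, although the general definition excludes that drug. The SAP does not say which sentence prevails.

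What is at stake is how the medication tables read. Hormonal contraceptives and tranexamic acid are prohibited during treatment, and Protocol 5.2.3.5 requires a woman prescribed tranexamic acid on treatment to be discontinued. If permitted follow-up use of these drugs appears in the concomitant table, it looks like on-treatment use that did not happen. It also defeats the separate presentation that the section asks for.

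**Working it through.** The plan gives no figure to reproduce; this is a date-classification rule. The check codes each sentence of SAP 7.3 as logic and applies it to every feasible pattern of dates.

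**Notation.** F = first dose, L = last dose.

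- General definition: start < L, and (end > F or ongoing).
- Cases: (1) start missing and end ≥ F; (2) start present and end missing; (3) both missing.
- Post-treatment: end > L, or ongoing.

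**Assumption.** A missing end date and an ongoing drug are stored the same way. The documents do not show how the eCRF codes ongoing use.

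**Patterns.** Four start positions (before F, on treatment, follow-up, missing) by four end positions (before F, on treatment, follow-up, missing or ongoing) give 4 × 4 = 16. Three have an end before the start and drop out, leaving 16 − 3 = 13.

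| Start | End | General definition | Any of the cases | Post-treatment |
|---|---|---|---|---|
| before F | before F | no | no | no |
| before F | on treatment | yes | no | no |
| before F | follow-up | yes | no | yes |
| before F | missing/ongoing | yes | yes (2) | yes |
| on treatment | on treatment | yes | no | no |
| on treatment | follow-up | yes | no | yes |
| on treatment | missing/ongoing | yes | yes (2) | yes |
| follow-up | follow-up | no | no | yes |
| **follow-up** | **missing/ongoing** | **no** | **yes (2)** | **yes** |
| missing | before F | no | no | no |
| missing | on treatment | no | yes (1) | no |
| missing | follow-up | no | yes (1) | yes |
| missing | missing/ongoing | no | yes (3) | yes |

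**Reading the table.**

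1. With a known start date, the two sentences conflict in one row only: start in follow-up, no end date. The general definition excludes the drug and case (2) includes it.
2. Where the start is before L and the end is missing, both sentences already give concomitant. Under the storage assumption, the only thing case (2) adds among drugs with a known start is those begun on or after the last dose.
3. A follow-up drug with a recorded end date is not concomitant under either sentence.
4. The conflicting row also meets the post-treatment definition, so the drug is listed twice, not moved from one table to the other. Double listing is right for a drug taken across the last dose; it is wrong here because there was no on-treatment use.

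**Which sentence would prevail?** Cases (1) and (3) have no start date, so neither can be shown to satisfy the general definition's start-date test. If that test also had to be met, those two cases could never classify anything. They must therefore work without it. Case (2) stands in the same list under the same lead-in, so the literal reading is that it also works without it.

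**Effect of the fix.** With start < L added to case (2), the conflicting row becomes post-treatment only. The other 12 rows are unchanged.

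**The case against.** The best defence is that the three cases are missing-date conventions to be applied inside the general definition. A drug with both dates recorded meets none of them, so they cannot be the whole rule and the general definition must still operate. The closing sentence on separate summaries shows the intent. This stands as evidence of intent, and a careful programmer might well code it that way. It does not remove the contradiction: cases (1) and (3) show that the list is meant to act where the start-date test cannot be met, and nothing exempts case (2).

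A second objection is that SAP 7.3 speaks both of drugs ongoing at the end of study and of end dates that are missing, and these may be different things. Case (2) may be meant only for end dates left blank. That also stands. If ongoing use is coded separately, the exposure shrinks to follow-up drugs whose end date was simply not recorded. Case (2) would still need the limit for those.

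A reader might infer three stronger things that the documents do not support.

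- *That follow-up hormones will be reported as on-treatment use.* This happens only if case (2) overrides the general definition and the storage assumption holds. The drug would still appear in the post-treatment table as well.
- *That the reading of bone or bleeding results is compromised.* The BMD analyses in SAP 9.5.2 do not use the concomitant classification to include, exclude or adjust; the exclusion they state concerns a change of scanner manufacturer. The bleeding impression scale in SAP 8.5.1 is analysed only within the placebo-controlled period, with no reference to medications. Prohibited use is assessed individually (Protocol 5.2.3.5), and protocol deviations are summarised in their own right (Protocol 8.1.5).
- *That the number of false entries can be estimated from the planned 500 women.* The documents give no rate for starting a drug in follow-up and no rate of missing end dates. SAP 7.3 also counts a woman once per preferred term, so an affected record need not add a count.

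**Conclusion.** The contradiction is real and minor. Within SAP 7.3, case (2) admits a drug that the preceding sentence excludes. Applied literally, it lists an open-ended drug begun in follow-up as both concomitant and post-treatment. One of 13 date patterns is affected.

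The wrong entry depends on two conditions: that case (2) is programmed as sufficient on its own, which is the more literal reading, and that ongoing drugs are stored with a missing end date, which the documents neither confirm nor rule out. Interim locks make the pattern more likely. SAP 2.5 and 2.6 bring follow-up data into those analyses, and a drug still in use at a cut-off would have no end date yet, even if one is recorded later.

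The consequence is limited to descriptive medication tables, where permitted follow-up use could be mistaken for prohibited on-treatment use. No test, BMD analysis or bleeding analysis changes, and the number of records cannot be estimated.

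**What to change.** Reword case (2) of SAP 7.3 so that it requires a known start date that is prior to the last dose of study drug, together with a missing end date. Use prior to, not on or before: the general definition uses the strict form, and a different boundary would create a new mismatch for drugs begun on the day of the last dose. Cases (1) and (3) need no change, since they have no start date to limit.

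The cost is one clause in the SAP and the matching line of table code. It needs no new data and does not affect trial conduct or any other analysis.
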